Arterial stiffness indices. We will measure **pulse wave velocity**, as done previously⁷. Tonometry pressure tracings will be obtained from the common carotid and ipsilateral common femoral artery (all recordings will be performed on the left side of the body). Time delays between pressure tracings will be calculated using the upswing of the pressure tracing²².

Pulse wave velocity²³ will be calculated as the direct distance between the probe and the thigh cuff divided by the time delay.

Biomarkers. Methodology for blood-based biomarkers is well-established in our research program. All venous blood samples will be collected into appropriate vacutainers, centrifuged, and serum/plasma separated. For purpose of screening, hemoglobin A1C, glucose, and lipids will be analyzed immediately in the investigator's lab (Afinion II, Cholestech LDX). All other samples will be stored at -80°C until delivery by courier to the Oregon Clinical and Translational Research Institute (OCTRI) at Oregon Health and Science University. OCTRI will analyze samples for fasted glucose and insulin (for the calculation of the homeostatic model assessment of insulin resistance (HOMA-IR). Samples collected for measurement of circulating biomarkers of cardiovascular health (IL-6, C-reactive protein, oxidized LDL, ET-1) and renal function (angiotensin II, plasma renin activity, aldosterone) will also be measured at OCTRI. A reduction in oxidized LDL will indicate reduced oxidative stress. Reduced C-reactive protein will indicate reduced systemic and vascular inflammation. HOMA-IR will be calculated using the available on-line calculator from the Oxford Center for Diabetes. Three 40mL blood draws will occur throughout the study immediately following the last void of the 24-hour urine collection during the Pre, Interim, and Post Tests.

24-hour Urine Collection. 24-hour urine collections are the gold standard for measuring basal kidney function (i.e., creatinine clearance, urinary albumin excretion, urinary sodium excretion). Subjects will be given two urine collection containers to take home. In our experience, subjects typically only need to use one container in a 24-hour period. Therefore, the second collection

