**Table 1. Outcomes by Protocol and Aim**

Protocol 1			
Outcomes	Aim 1	Aim 2	Aim 3
Primary	Clinic systolic and diastolic pressures; Ambulatory systolic and diastolic pressures	Pulse Wave Velocity (measure of arterial stiffness)	Acute and chronic pressure reductions
Secondary	Heart rate; Cardiac output; Stroke volume; Total peripheral resistance; Secondary BP outcomes: waking, sleeping, dipper vs. non-dipper	Blood-borne biomarkers	
Protocol 2			
	Cognitive	Brain biomarkers of ADRD risk	
Primary Outcomes	Memory domain composite score*	Arterial transit time: mean perfusion in gray matter, mean perfusion in white matter	

\*average of age-corrected list-sorting and age-corrected picture sequence z-scores

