**HEAT THERAPY VS EXERCISE TRAINING IN HYPERTENSION SAP**

dbp_dipper	Aim 1/Secondary	Categorical; non-dipper <10%, dipper ≥10% to <20%, and extreme dipper ≥20% change in diastolic BP at night calculated from ambulatory BP day and night averages
pwv	Aim 2/Primary	Continuous; average of three pulse wave velocity measurements collected at pre-, interim-, and post-intervention timepoints
il6_lg2	Aim 2/Secondary	Continuous; Biomarker IL-6 with the lower limit of detection (LLD) of 0.031 imputed for <LLD, log2 transformed for normalcy
crp_lg2	Aim 2/Secondary	Continuous; Biomarker CRP with the lower limit of detection (LLD) of 0.031 and upper LD (ULD) of 50 imputed for <LLD and >ULD, log2 transformed for normalcy
et1_lg2	Aim 2/Secondary	Continuous; Biomarker ET-1 with the lower limit of detection (LLD) of 0.031 imputed for <LLD, log2 transformed for normalcy
alb_lg2	Aim 2/Secondary	Continuous; Biomarker urine albumin with the lower limit of detection (LLD) of 0.031 imputed for <LLD, log2 transformed for normalcy
Supine.SBP.low	Aim 3/Primary	Continuous; average of three lowest consecutive supine systolic blood pressure measurements taken every 5 minutes for an hour post-intervention during supine recovery (for Heat Therapy: syst_bp55_ht_s1 to syst_bp110_ht_s1; for Exercise Training: for Heat Therapy: syst_bp55_ex_s1 to syst_bp110_ex_s1)
Supine.DBP.low	Aim 3/Primary	Continuous; average of three lowest consecutive supine systolic blood pressure measurements taken every 5 minutes for an hour post-intervention during supine recovery (for Heat Therapy: syst_bp55_ht_s1 to syst_bp110_ht_s1; for Exercise Training: for Heat Therapy: diast_bp55_ex_s1 to diast_bp110_ex_s1)
Supine.SBP.1.ch	Aim 3/Primary	Change from average pre-session resting SBP to Supine.SBP.low
Supine.DBP.1.ch	Aim 3/Primary	Change from average pre-session resting DBP to Supine.SBP.low
eGFR	Aim 1/Exploratory	eGFR was calculated using the CKD-EPI Creatinine-Cystatin Equation (2021) using the CKDEpi_RF.creat.cys function in the nephron R package and rounded to two decimal places
uacr	Aim 1/Exploratory	Urine albumin creatinine ratio (mg/g) was calculated by dividing urine albumin by urine creatinine/1000 rounded to 2 decimal places
Protocol 2		
cognitive_score	cognitive/Primary	Averaged z-scores (centered & divided by standard deviation) of age-corrected picture sequence score (age_cor_score)

		and age-corrected list-sorting score (list_age_cor_scpre)
--	--	--

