## 9 Efficacy Analyses

For primary analyses for Protocol 1 Aims 1, primary outcomes will be compared between groups (heat therapy vs exercise training) over time (within subject repeated measurements) using two-way repeated measures mixed model including an interaction between intervention group and timepoint with pre-defined contrasts. For Specific Aim 1, to test the hypothesis that heat therapy improves blood pressure (both in clinic and 24H ambulatory) better than dynamic aerobic exercise, the null hypothesis will be that the interaction between group and timepoint is equal to 0. For Aim 2, to determine whether heat therapy will improve biomarkers of arterial health (arterial stiffness & biomarkers of systemic

inflammation and oxidative stress) and compare responses to exercise training, the null hypothesis will be that the interaction between intervention group and timepoint is equal to 0. For Aims 1 and 2 exploratory analyses, ANCOVA will be performed for primary and secondary outcomes, with pretest values entered as a covariate and treatment condition specified as a fixed factor. Demographic and physiological variables (age, sex, BMI) and pre-intervention blood pressure will be added one at a time to the ANCOVAs to test for an interaction on treatment effects. For Aim 3, we will use ANCOVA models to determine the predictive potential of acute post-exercise hypotension response for chronic changes in blood pressure, with pretest values entered as a covariate and systolic and diastolic blood pressure specified as a fixed factor. Analyses will be performed on the Intention to Treat population. Additionally, change from pre- to post-intervention in ambulatory and in clinic systolic and diastolic pressure will be correlated with change from pre- to post first intervention session supine systolic and diastolic blood pressure by Pearson correlation.

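### The protocol defines pulse wave velocity, the Aim 2 primary outcome, with a time delay and a distance that end at different sites, and the SAP does not settle which is meant.

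*Protocol*

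**What the plan says.** The protocol's method is in section C, under the paragraph on arterial stiffness indices, and has four parts:

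- **Reference.** The method follows the group's earlier work: "We will measure pulse wave velocity, as done previously".
- **Recording sites.** "Tonometry pressure tracings will be obtained from the common carotid and ipsilateral common femoral artery", all on the left side.
- **Time delay.** "Time delays between pressure tracings will be calculated using the upswing of the pressure tracing".
- **Velocity.** PWV is the "direct distance between the probe and the thigh cuff divided by the time delay".

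SAP Table 1 (section 4.2) lists PWV as the single primary outcome for Aim 2. SAP Table 4 (section 5.5) defines the analysis variable as the "average of three pulse wave velocity measurements collected at pre-, interim-, and post-intervention timepoints", with no device, site or path length. For Aim 2, SAP section 9 states that "the null hypothesis will be that the interaction between intervention group and timepoint is equal to 0". Section 9.1 also enters PWV in exploratory correlations and a principal component analysis.

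**The concern.** PWV is a distance divided by the time the pulse takes to cover that distance, so both must refer to the same two points. As written, the delay ends at the femoral tonometry site and the distance ends at a thigh cuff. The quoted sentence is the only place where either document mentions a thigh cuff, and nothing says that a cuff recorded a waveform. It also speaks of one probe, although tonometry is described at two sites.

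No other measure in the plan would expose a scaling error. SAP section 4.2 says that β-stiffness, dynamic arterial compliance and other planned Aim 2 measures could not be collected. SAP section 6 gives effect sizes for several of those lost measures but none for PWV, so there is no documented PWV value to check against. Under SAP section 7.1 an externally contracted biostatistician does the final analysis, so the definition needs to be on paper.

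At stake are the absolute PWV values, the treatment effect in m/s, and the between-person analyses that use PWV. SAP section 9 also saves full model results for planning future studies and for meta-analysis, and those uses need a correct scale.

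**Working it through.** The documents give no distance, transit time or PWV value, so there is no plan figure to reproduce. The check is dimensional. All distances and velocities below are assumptions, shown as ranges.

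**Step 1: the factor.** Let L be the direct distance between the carotid and femoral tonometry sites, g the extra distance to the cuff, and t the carotid-femoral delay. Take the probe to be the carotid one.

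- Matched definition: PWV = L / t
- Literal text: PWV = (L + g) / t
- Ratio: k = (L + g) / L

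**Step 2: its size**, for an assumed true PWV of 8.0 m/s.

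| L (cm) | g (cm) | k | literal PWV (m/s) |
|---|---|---|---|
| 50 | 5 | 55/50 = 1.10 | 8.8 |
| 50 | 10 | 60/50 = 1.20 | 9.6 |
| 50 | 20 | 70/50 = 1.40 | 11.2 |
| 60 | 5 | 65/60 = 1.08 | 8.7 |
| 60 | 10 | 70/60 = 1.17 | 9.3 |
| 60 | 20 | 80/60 = 1.33 | 10.7 |

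**Step 3: a factor common to all participants and visits.** Suppose the true between-group difference in change is -0.50 m/s with SD 1.0.

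- k = 1.1 gives -0.55, k = 1.2 gives -0.60, and k = 1.4 gives -0.70 m/s.
- The SD is multiplied by the same k, so the standardised effect is (k × -0.50) / (k × 1.0) = -0.50 each time.
- The group-by-timepoint test is therefore unchanged. Only the estimate in m/s moves, and Table 4 lists PWV untransformed.

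**Step 4: a factor that differs between people but is fixed within each person.** It does not cancel in between-person analyses, because part of the spread in PWV is then spread in cuff position. This reaches the correlations and principal component analysis in SAP section 9.1.

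**Step 5: a factor that differs between visits.** It enters within-person change directly.

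- A 1 cm shift in the measured distance changes the literal value by 1/(L + g): from 1/80 = 1.3% to 1/55 = 1.8%.
- A 2 cm shift at L = 50 cm and a true 8 m/s changes it by 8 × 0.02 / 0.50 = 0.32 m/s.
- The protocol does not say whether the distance is measured once or at each visit.

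**Step 6: the other readings.** If a cuff recorded the distal waveform, both distance and delay end at the cuff. If the distance in fact ran to the femoral site, both end there. In either case k = 1.00.

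**The case against.** A reader might infer that the recorded velocities are wrong. The documents do not support that, because they do not show which sensor captured the distal pulse. The single probe paired with a cuff would fit a device in which the cuff takes the distal waveform; the tonometry sentence would then be the loose one. Alternatively, the cuff wording may be carried over from another text. The same paragraph cites references 22 and 23, while the reference list as available ends at 15, which makes a wording slip plausible. The earlier publication it relies on cannot be consulted here. This objection stands, and any claim of numerical error has to be conditional.

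A reader might also infer that the Aim 2 comparison of heat therapy with exercise is biased. That does not follow either. Both arms use the same method, a common factor leaves the test unchanged, and no planned analysis compares PWV with an outside value or threshold. Noise from cuff placement is a possibility only, since nothing says that the cuff or the distance was reset at each visit, and re-measuring any path length would add similar noise.

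The objection does not remove the contradiction. Under every reading, at least one of two adjacent sentences defining a primary outcome is wrong or incomplete. Citing an earlier method does not make them agree, and the SAP does not choose between them.

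**Conclusion.** The concern holds as an internal inconsistency in the definition of the Aim 2 primary outcome. It does not establish a measurement error.

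If the text was followed literally, PWV is too high by (L + g)/L, about 8% to 40%. The upper end is the extreme corner of the assumed range (20 cm on 50 cm). Effects in m/s would be inflated by the same factor if it is common to everyone, with no change to the group-by-timepoint test. Variation in the factor between people would affect the PWV correlations, and variation between visits would cost precision in within-person change. If a cuff recorded the distal pulse, or the distance ran to the femoral site, the error is zero and only the wording needs repair.

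The percentages rest wholly on the assumed distances. The contradiction rests on the text alone. It should be corrected, because it concerns a primary outcome and the correction is cheap.

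**What to change.** 1. Confirm from laboratory records which device and which two sites gave the time delay, and where the distance was measured.
2. In protocol section C, define PWV as the direct distance between the two sites that give the time delay, divided by that delay. The sites are the carotid and femoral tonometry sites or, if the cuff recorded the distal waveform, the carotid site and the cuff. Correct whichever sentence is wrong.
3. State that one distance per participant is used at the pre, interim and post tests.
4. Put the same definition in the PWV row of SAP Table 4.
5. Recompute PWV from the recorded distances only if the literal formula was used.

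The cost is about one sentence in each document and a check of the records. Recomputation arises in only one of the three readings and requires that the distances were recorded.

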responsible for many of the changes observed with aging, are key risk factors for other major clinical disorders, and are increasingly implicated in cognitive declines with aging and risk of ADRD. Importantly, it has been reported that the frequency of sauna bathing was associated with lowered risks of dementia and Alzheimer's disease¹⁰. The results of these studies suggest that heat therapy may reduce the risk of hypertension and dementia either independently or through reductions in systolic blood pressure but are confounded by other factors such as greater sauna use by individuals with higher income, education and discretionary time. The effects of heat therapy on cardiovascular health and cognitive function are best determined by randomized clinical research trials. Notably, women were not included in previous studies, and we have substantial preliminary data demonstrating that women are showing all of the same benefits of heat therapy as men. Heat therapy represents a possible lifestyle intervention that, as our preliminary findings suggest, may be more effective in lowering systolic blood pressure and reducing arterial stiffness than aerobic exercise training, which is known to slow/delay the development of normal cognitive aging. Therefore, the purpose of Protocol 2 is to determine the potential of heat therapy in middle-life individuals with hypertension to improve cognitive function and MRI-based markers of ADRD risk.

B. Specific Aims/Study Objectives

Protocol 1:

The overarching goal of this research is to perform a clinical trial to determine whether heat therapy improves blood pressure and vascular health in HTN.

Specific Aim 1: Utilizing a prospective randomized clinical trial study design, we will determine whether heat therapy improves blood pressure (both in clinic and ambulatory) better than dynamic aerobic exercise, the gold-standard non-pharmacological treatment of essential HTN. Specifically, we hypothesize that 30 sessions of passive heat therapy using hot water immersion over 8-10 weeks will improve blood pressure in HTN individuals to a greater extent than 30 sessions of exercise training over the same time period.

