INTERVENTION	
Last 15 sessions

General workflow for the protocol. The table at the right depicts the workflow for this clinical trial protocol, which is as follows:

RECRUIT: The trial will be conducted in a cohort of physically inactive to moderately active men and women with high blood pressure (Elevated and Stage 1 or 2 Hypertension, based on current guidelines)⁴ from the local Eugene and Springfield, OR communities (details under section D). Potential subjects will be pre-screened by phone to determine eligibility.

POST-TESTS

- Hemodynamic tests
- Biomarkers
- 24-h Ambulatory blood pressure
- 24-h Urine collection
- VO₂Peak Test

PRE-SCREEN: Candidates will complete a pre-screening consent and answer pre-screening questions online and over the phone. If candidates appear to qualify, they will be further screened for eligibility over the phone using the IPAQ.

SCREEN: Subjects will need to come to the laboratory on two separate occasions as part of the initial screening process. Seated blood pressure will be measured on two separate screening visits to determine resting blood pressure. During each visit, blood pressure will be measured twice, performed according to clinical guidelines for assessing hypertension⁴. The average blood pressure of these four readings obtained over two assessments must fall within the inclusion criteria range to qualify for inclusion in the study. If the average blood pressure of these four readings (two obtained during Screening Day 1 and two obtained during Screening Day 2) does not fall within the allowable limits for this study, the subject will be excluded from the study. During Screening Day 1, the informed consent process will be completed for Protocol 1. We will also assess medical history, BMI, fasting glucose, hemoglobin A1c, and lipid profile to verify eligibility. If the subject is interested in participating in Protocol 2, the informed consent process for Protocol 2 will be completed on Screening Day 2 and the subject will be pre-screened using the MRI PRE-SCREENING FORM, LCNI MRI SAFETY SCREENING QUESTIONNAIRE and MMSE. Subjects who undergo screening and satisfy all inclusion criteria and no exclusion criteria will be enrolled in the study and progress to a battery of pre-intervention tests (PRE-TESTS).

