Projected effect sizes and statistical power. To estimate effect size for the primary outcome variables of systolic and diastolic blood pressures, we bracketed over several scenarios with varying pre- to post-intervention differences (i.e., with the fall in pressure following heat therapy being 4.0, 4.5, or 5.0 mmHg greater than following exercise training), and using a SD of 4.5 mmHg from our pilot work and published studies using similar interventions and approaches, which resulted in minimum hypothesized effect sizes of 0.89, 1.00, and 1.11 for Aim 1. Effect sizes for blood pressures were the lowest of our outcome variables; thus, powering for blood pressure will allow adequate power for numerous measurements giving us a global picture cardiovascular and autonomic health. Our prospective power estimates based on a simpler model (two-sample RCT design, modeled as a two-sample t-test), to detect a minimum hypothesized effect size of 0.89 (which is smallest effect size of interest across outcome variables; power 90%; $\alpha=0.05$), indicate the need to enroll 50 subjects (50:50 ratio of study groups; sample size assumes 20% dropout for the per-protocol analysis). Of those preliminarily screened who appear to be eligible, we will consent and enroll up to 250 individuals for further screening for eligibility anticipating only 50 individuals will be eligible for participation in the study. We need 50 study participants to account for rate of attrition once participants are enrolled in the formal study to ensure completion of 40 participant needed for statistical purposes.

D. Research Population, Recruitment Methods, and Compensation

Protocol 1:

The trial will be conducted in a cohort of 50 physically inactive to moderately active men and women with high blood pressure (Elevated, Stage 1, and Stage 2, based on current guidelines)⁴ from the local Eugene and Springfield, OR communities. We will attempt to recruit subjects that represent the ethnicity of Eugene, Oregon and the University of Oregon.

Subjects will be recruited locally (newspaper advertisements, flyers, radio advertisements, in-person recruitment events, online posts, as well as Craigslist and other online advertisements including ad campaigns designed and hosted by marketing companies), as well as referred to us by local physicians and clinics.

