## 6 Sample Size

**Projected effect sizes.** To estimate effect size for the primary outcome variables of systolic and diastolic blood pressures, we bracketed over several scenarios with varying pre- to post-intervention differences (i.e., with the fall in pressure following heat therapy being 4.0, 4.5, or 5.0 mmHg greater than following exercise training), and using a SD of 4.5 mmHg from our pilot work and published studies using similar interventions and approaches, which resulted in minimum hypothesized effect sizes of 0.89, 1.00, and 1.11 for Aim 1. For MSNA, we used a pre-intervention mean value of 39 $\pm$ 7 bursts/100beats based on our pilot data with 4 HTN subjects, and determined that a post-intervention mean value of 29 $\pm$ 7 b/100bts would represent a clinically significant change (of 10 b/100bts). Thus, for MSNA,  $d = 1.43$ .

Similarly, from our pilot work and our published studies using similar interventions and approaches, calculated effect sizes for  $\beta$ -stiffness  $d = 1.43$ , DAC  $d = 1.70$ , sympathetic baroreflex  $d = 1.33$ , FMD  $d = 2.55$ , carotid wall thickness  $d = 3.33$ , for Aim 2. Effect sizes for blood pressures were the lowest of our outcome variables; thus, powering for blood pressure will allow adequate power for numerous measurements giving us a global picture cardiovascular and autonomic health.

**Statistical power.** Our prospective power estimates based on a simpler model (two-sample RCT design, modeled as a two-sample t-test), to detect a minimum hypothesized effect size of 0.89 (which is smallest effect size of interest across outcome variables; power 90%;  $\alpha=0.05$ ), indicate the need to enroll 50 subjects (50:50 ratio of study groups; sample size assumes 20% dropout for the per-protocol analysis).

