### 7.2 Analysis Populations

Intention-to-Treat will be the primary analysis approach. However, as one goal is to compare outcomes when subjects maintain compliance with heat therapy and exercise training, we will also employ per-protocol analysis as a secondary approach, including subjects with  $\geq 90\%$  compliance. As an exploratory step, we will conduct analyses of variance to compare characteristics of dropouts vs. completers, as this may inform future endeavors.

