#### 7.2.1 Intention to Treat or Modified Intention to Treat

- *All participants who received any intervention and who participated in at least one post-baseline assessment*

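### The stated 90% power does not follow from the plan's inputs: at d = 0.89, 40 completers give 78% power two-sided or 87% one-sided

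*Protocol*

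**What the plan says.** The power paragraph in Protocol section C takes differences between arms of 4.0, 4.5 and 5.0 mmHg with an SD of 4.5 mmHg, giving effect sizes of 0.89, 1.00 and 1.11. It then treats the trial as a two-sample t-test at the smallest of these, with 90% power and alpha 0.05, and concludes that these inputs "indicate the need to enroll 50 subjects (50:50 ratio of study groups; sample size assumes 20% dropout for the per-protocol analysis". It explains that 50 participants are needed "to ensure completion of 40 participant needed for statistical purposes".

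SAP section 6 repeats the effect size ("which is smallest effect size of interest across outcome variables; power 90"%), the alpha, the 50 enrolled and the 20% dropout. It does not repeat the sentence about 40 completers.

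Neither text says whether alpha is one- or two-sided. Two other places bear on this:

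- Protocol section B, Specific Aim 1, is directional: heat therapy "will improve blood pressure in HTN individuals to a greater extent than 30 sessions of exercise training".
- SAP section 9 gives the Aim 1 null in two-sided form: "the null hypothesis will be that the interaction between group and timepoint is equal to 0".

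On who is analysed, SAP 7.2 says "Intention-to-Treat will be the primary analysis approach", with per-protocol secondary. SAP 7.2.1 defines the primary set as "All participants who received any intervention and who participated in at least one post-baseline assessment". In Protocol section C (SCREEN), eligible subjects "will be enrolled in the study and progress to a battery of pre-intervention tests". Enrolment therefore comes before randomization, and 50 is the upper limit of the primary analysis set.

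**The concern.** Every input to the power calculation except sidedness is stated, so the 90% can be checked directly. For a standardised difference of 0.89, 20 per arm looks too few for 90% power.

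This is the only power figure in either document. Both texts also say that blood pressure has the smallest effect size, so that powering for it covers the other measurements. The figure therefore carries beyond Aim 1. A reader who meets a null heat-versus-exercise result and relies on 90% power would take it as stronger evidence against a 4.0 mmHg advantage than the design's inputs support.

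**Working it through.** **Inputs** (Protocol C, power paragraph; SAP 6): difference 4.0 mmHg, SD 4.5 mmHg, d = 4.0/4.5 = 0.889, stated as 0.89; alpha 0.05; 1:1 allocation; 20% dropout; 50 enrolled; 50 × 0.8 = 40 completers. Sidedness is not stated, so both are shown. The range of 40 to 50 analysed is an assumption about how many of those enrolled contribute data.

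**Method.** Power of the two-sample t-test from the noncentral t distribution, with noncentrality δ = d·√(n₁n₂/(n₁+n₂)) and df = n₁+n₂−2. Power is the probability that t exceeds its critical value (two-sided 5% or one-sided 5%).

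**The plan's own case, 40 completers (20/20).** δ = 0.89 × √10 = 2.814, df = 38.

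- Two-sided, critical value 2.024: power 78.3%.
- One-sided, critical value 1.686: power 86.8%.

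The stated 90% is not reproduced under either sidedness.

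**Other numbers analysed (d = 0.89).**

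| Analysed | Split | δ | Two-sided | One-sided |
|---|---|---|---|---|
| 40 | 20/20 | 2.814 | 78.3% | 86.8% |
| 45 | 22/23 | 2.984 | 83.1% | 90.2% |
| 50 | 25/25 | 3.147 | 86.9% | 92.7% |

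**Number needed for 90% at d = 0.89.**

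- Two-sided: 28 per arm, so 56 completers; 56/0.8 = 70 enrolled.
- One-sided: 45 completers as 22/23 (45/0.8 = 56.25, so 57 enrolled), or 46 with equal arms (46/0.8 = 57.5, so 58 enrolled).

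**Check by the normal approximation**, n per arm = 2(z_α + z_β)²/d², with d² = 0.7921.

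- 90%, two-sided: 2 × (1.960 + 1.282)²/0.7921 = 26.5.
- 90%, one-sided: 2 × (1.645 + 1.282)²/0.7921 = 21.6.
- 80%, two-sided: 2 × (1.960 + 0.842)²/0.7921 = 19.8, which rounds up to 20 per arm, 40 completers and 40/0.8 = 50 enrolled.

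The cruder method does not rescue the figure: at 40 completers it gives 80.4% two-sided and 87.9% one-sided. The last line does match the plan's 40 and 50 exactly, so the slip may lie in the power label. That is an inference; the documents do not say so.

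**The plan's three scenarios with 40 completers.**

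| Difference | d | Two-sided | One-sided |
|---|---|---|---|
| 4.0 mmHg | 0.889 | 78% | 87% |
| 4.5 mmHg | 1.00 | 87% | 93% |
| 5.0 mmHg | 1.11 | 93% | 96% |

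**Difference detectable with 90% power (d × 4.5 mmHg).**

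- Two-sided: 1.052 × 4.5 = 4.73 mmHg (40 analysed); 0.936 × 4.5 = 4.21 mmHg (50).
- One-sided: 0.942 × 4.5 = 4.24 mmHg (40); 0.840 × 4.5 = 3.78 mmHg (50).

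**The case against.** Four points can be made for the plan.

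1. **The primary set may exceed 40.** The 20% dropout is tied to the per-protocol analysis, which is secondary. Someone who leaves after the interim tests stays in the primary set, and with all 50 analysed a one-sided t-test gives 92.7%. This stands and is why both ends of the range are shown. It does not reproduce the plan's calculation, because the protocol itself names 40 completers as the number needed, and 40 falls short under either sidedness.

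2. **Sidedness is open.** The null in SAP section 9 belongs to an interaction in a mixed model with three timepoints, so it does not settle which test the planning calculation used, and the hypothesis is directional. This stands. One-sided, the chance of missing 4.0 mmHg runs from 7% (50 analysed) to 13% (40), a range that includes the 10% implied by the plan.

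3. **The 90% belongs to a simpler model.** The planned repeated-measures analysis could be more powerful. That is possible, but the documents give no within-subject correlation from which to calculate it, and they attach the 90% to the t-test. The shortfall shown is in that stated calculation and is not a demonstrated property of the primary analysis.

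4. **It is late.** SAP sections 8.2 and 13 show that data had already been examined, so the sample size can no longer respond. This limits the point to correct reporting of the design. It does not make the 90% correct.

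**Conclusion.** The concern holds. Under the plan's own inputs, 40 completers give 78.3% power two-sided or 86.8% one-sided, so the stated 90% is missed by about 12 or 3 percentage points. It is reached only with a one-sided test and about 45 or more analysed; two-sided, even all 50 give 86.9%. The two-sided chance of missing a true 4.0 mmHg advantage is 13.1% (50 analysed) to 21.7% (40 analysed), up to about twice the 10% implied.

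This rests on the plan's d of 0.89, SD of 4.5 mmHg, equal arms and the t-test it names, and on between 40 and 50 participants being analysed. It should be fixed because the figure is wrong as written in both documents. The effect is on the stated design properties only.

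**What to change.** Keep 50 enrolled and the 4.0/4.5/5.0 mmHg scenarios. Add a dated correction to the power paragraph in Protocol section C and to SAP section 6, logged in SAP section 13. If the planning calculation is on file, retrieve it first and add the sidedness and power it used. Suggested text:

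> This section stated 90% power without saying whether the test was one- or two-sided. Under the simplified two-sample t-test (two-sided alpha 0.05, SD 4.5 mmHg), 50 enrolled participants give about 78% power for a 4.0 mmHg difference if 40 are analysed and about 87% if all 50 are analysed (one-sided: about 87% and 93%). Two-sided power of 90% corresponds to a difference of about 4.7 mmHg with 40 analysed or 4.2 mmHg with 50. These figures describe the simplified test, not the planned mixed model.

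The cost is wording only: no extra participants and no change to the model, test, populations or outcomes. The one drawback is that the stated power becomes less favourable.
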